- ERQ13 To conduct a latent class mediation analysis to explore how the volume of violent offences is mediated by the frequency and type of substance used at 6 and 12 months.

Part of this work will be to examine the potential impact of both UK and region-specific issues that may be linked to race, ethnicity, sex, socioeconomic factors and other considerations that may arise which are connected to EDI.

Internal pilot study

Prior to embarking on the efficacy study an internal pilot study will be undertaken. The aim of the internal pilot study is to explore whether it is feasible to deliver MDFT in the UK context and establish key parameters to incorporate into the design of the efficacy study. Progression criteria are detailed in appendix II and the study will be conducted between September 2025 with a transition decision in June 2026.

In the pilot study we will recruit 60 participants, 30 in each arm, across the 2 sites. This will allow for exploration of key parameters needed to confirm sample size calculation for the efficacy study. It is sufficient to allow estimation of two-sided 95% CIs around the proportions of eligible, consenting, adhering and followed up at month 6 in each arm of the study with half-widths less than 0.15. It meets the 30 per group recommended by Lancaster et al (Lancaster et al., 2004) for estimating the SE of a primary outcome with sufficient precision, including accounting for any variation across site, where 12 participants per arm per site is recommended.

Objectives for the internal pilot trial

- **PRQ1** To conduct a prospective, two-arm, individually randomised RCT to pilot study outcomes and methods and establish the parameters for the conduct of efficacy evaluation.
- **PRQ2** To assess whether progression criteria have been met and develop an appropriately powered efficacy protocol.
- **PRQ3** To confirm the pre- post-test correlation on the primary outcome, percent days abstinent from alcohol and/or drugs to incorporate into a sample size calculation.
- **PRQ4** To estimate an estimate of potential effect for the primary outcome for inclusion in a sample size calculation.
- PRQ5 To explore the relationship between the use of alcohol and specific drugs and violent offending. This will be achieved through an analysis of existing datasets; Reframe and RISKIT-CJS, with a confirmatory analysis conducted on the pilot data at the time of transition.

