On completion of assessment battery research staff receive automated message of a referral, randomisation conduct, allocation relayed back to Barnardo's staff who either initiate MDFT or make referral to BAU.

Randomised to BAU (200) Randomised to MDFT (200)

YP referred to alternative service YP allocated MDFT therapist

Outcome assessment at month 6 Outcome assessment at month 6 (n=182) (n=182)

Outcome assessment at month 12 Outcome assessment at month 12 (n=160) (n=160)

Data is collected at 6- and 12-months using bespoke, secure, on-line data collection system and transferred to secure servers managed by the University of Kent. Six- and 12-month data collection is completed by research staff blind to participant allocation and participants receive a payment of £25 for completing assessments at baseline 6- & 12 months.

Sample size calculations

Sample size estimation was conducted in STATA18. A clinically important effect size for substance use frequency in adolescents is estimated as 0.27, similar to the lower bound

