estimates found in systematic reviews of MDFT (Filges T. et al., 2018, van der Pol et al., 2017b). This equates to a number needed to treat of 6, where at least one in six participants receiving MDFT would show clinically important benefits, and a difference in the frequency of substance use of at least 13% in the MDFT group. Detecting an effect size smaller than this provides no additional benefit, the commissioning of services in England and Wales requires the service to achieve a clinically important difference for the target population. To detect this difference, with power at 80% and alpha of 0.05 and a two-tailed test, requires a sample of 480 participants followed-up at the 6-month endpoint. Using data from other studies of substance using adolescents (Coulton S et al., 2023, Deluca et al., 2020) we estimate the prepost-test correlation of the frequency of substance use to be 0.4, and incorporating this into the sample size calculation reduces the number followed-up to 364, 182 in each group. Assuming a loss to follow-up at the endpoint of 10%, similar to other studies in adolescent substance use populations (Coulton et al., 2024) inflates the number needed to randomise to 400. Assuming 80% of those eligible will be willing to consent an indication of acceptability of the study to participants and a lower figure than other studies in similar populations (Coulton et al., 2024) would mean we would need to approach 480 across both sites. Recruitment will be continuous between September 2025 and January 2027, 28 per month will need to be approached in total across both sites per month with the expectation that 24 will consent to participate in the trial across both sites. We anticipate. Based on relative population size that 40% of referrals will come from Newport and 60% from Bristol.

Table 2: Recruitment/ retention table

	Q1	Q2	Q3	Q4	Q5	Q6	Q7	Q8	Q9	Q10	Q11
Months (e.g. Oct-Dec 23):	May-Jul 25	Aug-Oct 25	Nov 25 - Jan 26	Feb - Apr 26	May-Jul 26	Aug-Oct 26	Nov 26 - Jan 27	Feb - Apr 27	May-Jul 27	Aug-Oct 27	Nov 27 - Jan 28
Target number of children and young people referred into the project	0	50	75	75	75	75	75	75	218	360	500
Target number of children and young people recruited to the project and evaluation	0	40	60	60	60	60	60	60	174	288	400
Target number of children and young people who withdraw/drop out	0	4	6	6	6	6	6	6	23	35	40

Table 3: Sample size calculations

		PARAMETER		
Minimum Detectable Effect Size (MDES)		0.27		

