Compliance

We will assess adherence using the MDFT clinical portal, this assesses the dose and duration of interventions planned and delivered including the specific domains targeted at each session. A minimum dose of MDFT is defined as completion of the following metrics over a 6-month period.:

- Adolescent-only Sessions: 55% of total sessions being completed.
- Family Sessions: 30% of total sessions (includes the time within family sessions when therapist might have a little one on one time with youth or parent if needed).
- Parent/ carer-only sessions: 15% of total sessions (maybe with a single parent/ carer alone, and/ or time with the parenting team/ system together.

We plan on conducting a secondary analysis using a Complier Average Causal Effects (CACE) model using an instrumental variable framework. CACE analysis allows us to avoid bias by weighting the ITT treatment effect by compliance with the intervention or control treatment received, this provides an unbiased estimate of the role of compliance in the outcomes observed. By using different thresholds of compliance, a minimum threshold of 12 sessions over 4 months versus complete compliance, we can explore the nature of the relationship between compliance with the intervention and outcomes observed.

Analysis

Pilot study analysis

In the pilot study we will explore the distributional assumptions for each outcome measure and present descriptive statistics, either parametric or non-parametric overall, by allocated group and by stratification variables. We will estimate likely proportions of participants who are eligible, consent and followed up at 6 months. Each of these will be assessed against progression criteria detailed in appendix I (**PRQ1**, **PRQ2**).

We will conduct a descriptive analysis of outcomes including measures of central tendency and estimates of precision for continuous outcomes and proportions for categorical outcomes. Inferential analysis at the pilot stage will focus on the primary outcome and will involve a futility analysis using a fractional regression adjusted for stratification variables. This will allow us to confirm or revise our sample size calculation (**PRQ3, PRQ4**).

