We will explore the relationship between alcohol and substance use and violent offending (**PRQ5**) by comparison of data derived from the TLFB for specific substances and the SRDS. This will enable decisions to be taken about whether specific substances should be the target of the efficacy trial. Data redundancy (**PRQ6**) will be explored by examining the pattern of missing data for each outcome.

We will explore business as usual (PRQ7) through interviews with key stakeholders across both sites, those that deliver business as usual and those that refer to their services. We will explore key questions around acceptability of the intervention, factors that facilitate or hinder participation, intervention delivery and outcome assessment (PRQ8, PRQ9) by conducting interviews with young people and parents/ carers, purposively sampling those who did not consent and those who consented but dropped out of the intervention or follow up. To explore how the intervention is sensitive to the sociocultural needs of the target population and determine potential culturally influenced barriers towards the acceptability of the intervention in relation to ethnicity and equity, as well as the presence of structural barriers, we will conduct in-depth qualitative interviews with young people from minority ethnic communities and other marginalised groups including those with SEND and LAC, as well as with staff, and providers. Thematic analysis (Braun and Clarke, 2006) will be used to elicit young people's experiences of the programme, in addition to staff, and service providers' perspectives, and how these experiences impact on the acceptability of the intervention. The findings will inform future adaptations of the intervention to various socio-cultural contexts.

Efficacy study analysis

The primary analysis will take the form of a fractional regression model, adjusted for baseline stratification variables and the baseline covariate.

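### The pilot futility model leaves out the baseline substance-use covariate that the sized efficacy model includes, so its effect estimate is slightly less precise than it need be and it does not itself supply the PRQ3 correlation

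*Protocol*

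**What the plan says.** Protocol, Pilot study analysis: inference at the pilot stage is confined to the primary outcome and consists of "a futility analysis using a fractional regression adjusted for stratification variables". The next sentence says this will serve to confirm or revise the sample size, and cites PRQ3 and PRQ4. The strata are site and GAIN-SS severity (Table 1 and Randomisation).

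Protocol, Objectives for the internal pilot trial: PRQ3 is "To confirm the pre- post-test correlation on the primary outcome", for use in a sample-size calculation. PRQ4 is to estimate the effect on the primary outcome for the same use.

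Protocol, Efficacy study analysis: the primary model is a fractional regression "adjusted for baseline stratification variables and the baseline covariate".

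Protocol, Sample size calculations: the target effect is set out first ("A clinically important effect size for substance use frequency in adolescents is estimated as 0.27"). The test is then specified ("with power at 80% and alpha of 0.05 and a two-tailed test"). The correlation comes from earlier studies in similar adolescents: "we estimate the prepost-test correlation of the frequency of substance use to be 0.4". Its effect on the target is stated in the same section: "incorporating this into the sample size calculation reduces the number followed-up to 364, 182 in each group".

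Table 1 gives the baseline for the primary outcome as percent days abstinent from a single substance use question over 28 days. The Primary outcome section and Table 4 show that question being asked at baseline, so it is available for every pilot participant.

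**The concern.** The protocol names two adjustment sets for the same outcome. The larger set is the one behind the 364. The smaller set is used in the pilot, where the estimate is meant to inform futility and the sample size. The wording of the efficacy section separates stratification variables from the baseline covariate, so the pilot sentence cannot easily be read as including both.

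Two things follow. First, the pilot effect estimate carries outcome variation that a baseline value already in hand would remove. Second, the regression that is credited with answering PRQ3 contains no baseline measure of the outcome, and the section describes no other step that produces the correlation. That correlation matters because the 364 is sensitive to it.

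**Working it through.** **Inputs.** Standardised effect 0.27, two-sided alpha 0.05, power 80%, r = 0.4 and loss to follow-up 10% (Sample size calculations). Pilot of 60, 30 per arm (Internal pilot study), so 60 × 0.9 = 54 followed up. Allocation 1:1 (Randomisation). Outcome SD is set to 1, and a linear model stands in for the fractional regression.

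**1. The plan's own figure.** Per arm, n = 2(1.960 + 0.842)² × (1 − r²) / 0.27².
- With r = 0.4, 1 − r² = 0.84 and n = 181 per arm, 362 in total. The t-based version gives 216.3 × 0.84 = 181.7, so 182 per arm and 364. The stated 364 reproduces.
- Without the covariate, n = 216 per arm, 432 in total (434 t-based). The protocol's unadjusted figure ("requires a sample of 480 participants followed-up at the 6-month endpoint") does not reproduce as a number followed up. It equals 432 / 0.9, the number to randomise. That is a separate matter, but it confirms that the 364 rests on the r = 0.4 adjustment.

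**2. Sensitivity of the target to r** (number followed up, same formula):

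| r | N |
|---|---|
| 0.2 | 414 |
| 0.3 | 392 |
| 0.4 | 362 |
| 0.5 | 324 |
| 0.6 | 276 |

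**3. Precision of the pilot estimate.** SE = √(4/54) = 0.272 without the covariate, and √(4 × 0.84/54) = 0.249 with it. The ratio is 1/√0.84 = 1.091, a 9% larger SE. This gives no credit for severity stratification.

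**4. Credit for the GAIN-SS stratum.** The protocol does not say how closely GAIN-SS severity tracks baseline frequency of use, so a range was simulated (linear model, 54 participants, allocation balanced within site and severity, 4,000 runs per setting).

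| Latent correlation, severity with baseline use (assumed) | SE, strata only | SE, strata plus covariate | Ratio |
|---|---|---|---|
| 0 | 0.272 | 0.252 | 1.08 |
| 0.5 | 0.272 | 0.256 | 1.06 |
| 0.9 | 0.261 | 0.253 | 1.03 |

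Together with step 3, the avoidable inflation is about 3% to 9%.

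**5. Effect on a futility reading.** The chance that the estimate is at or below zero when the true effect is 0.27 is Φ(−0.27/0.272) = 16.1% without the covariate and Φ(−0.27/0.249) = 14.0% with it.

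**6. What the pilot can say about r.** Fisher z: atanh(0.4) = 0.424, with SE 1/√(54 − 3) = 0.140. The 95% interval for r is about 0.15 to 0.60. Put into the formula in step 1, it corresponds to about 422 down to 274 followed up.

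**The case against.** The strongest reply is that PRQ3 does not need the regression. A pre-post correlation can be computed directly from the baseline question and the month-6 timeline follow-back. The protocol also builds its sample size in two steps, an unadjusted number and then a reduction for r, so what has to be rechecked is the outcome variance and r, and the pilot collects both. Adding a covariate to a fractional regression would not help PRQ3 anyway: that model returns a coefficient on a link scale, not a correlation and not the linear-model residual variance behind the 364. All of this stands. A reader might infer that the pilot cannot confirm the sample size at all. The documents do not support that.

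A reader might also infer a loss of power from 80% to 73% at 364, or that the check would call for about 69 more participants followed up (431 against 362). Neither follows. The first describes a full trial analysed without the covariate, whereas the Efficacy study analysis includes it and pools the pilot participants into that model. The second requires the team to resize from the unadjusted variance and then ignore r, contrary to PRQ3 and to the protocol's own method. Likewise, a one-SD chance baseline imbalance would move the unadjusted pilot estimate by 0.4 × 0.272 = 0.11 SD, but that movement is already part of the SE of 0.272 and is no additional harm.

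Finally, no progression criterion in Appendix II uses the pilot treatment effect, and details of sample-size re-estimation often sit in a statistical analysis plan. That limits the consequence. It does not remove the point, because the protocol itself fixes the pilot adjustment set and credits that model with PRQ3.

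**Conclusion.** The point holds in a limited form. The pilot estimate used for futility and PRQ4 comes from a different model than the one that was sized, and its SE is about 3% to 9% larger than necessary. This is random error, not bias, because allocation is randomised. The futility reading changes little (16% against 14%), and the power and estimate of the main trial are unaffected. As written, no step in the pilot analysis produces the correlation that PRQ3 asks for, although the data for it will exist.

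The sizes assume r = 0.4, 54 followed up, a linear approximation to the fractional model, and an unknown association between GAIN-SS severity and baseline use. Even after the change, the pilot confirms r only weakly, with an interval of about 0.15 to 0.60. The reason to act is that the improvement is almost free.

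**What to change.** In Pilot study analysis, adjust the pilot fractional regression for the stratification variables and the baseline covariate (percent days abstinent derived from the single substance use question), so that it matches the Efficacy study analysis.

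Add a sentence for PRQ3: the correlation between baseline and month-6 percent days abstinent will be estimated directly, reported with its 95% confidence interval, and that value carried into the calculation under Sample size calculations. It should not be taken from the fractional regression.

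The cost is one or two sentences and one degree of freedom in the pilot model. No new data are needed.

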Staff at Barnardo's will screen referrals to ensure they are consistent with the study inclusion and exclusion criteria and take informed consent. The principle of Gillick consent will be employed by staff trained in assessing Gillick competence to assess whether participants are mature and intelligent enough to make their own informed decisions. As a rule, young people aged 13 years or more, of average intelligence, are considered Gillick competent. Unless there is a specific reason not to do so, parents/ carers will be informed of the young person's participation in the study. Where consent cannot be taken using the Gillick principle, consent will be sought from a person with parental responsibility, in this scenario if a parent/ carer provides consent the young person will also have to provide assent to ensure there is no parental coercion to participate. Parent/carer consent is not required at the start of delivery. MDFT therapists will work with the young person to build their trust in the process and comfort with seeking parental/carer consent. They will also work to identify a trusted adult that could take the place of a parent/carer where needed. Broadly speaking, we would expect parents to be approached within a month of the young person starting MDFT. Giving young people the time and space to decide whether to approach a trusted adult, who it may be, and how they may approach them is crucial to the rapport building process.

It is anticipated that 60% of the referrals will come from Bristol and 40% from Newport, based on the relative population sizes. This means that 4 therapists will be recruited in Bristol and 3 in Newport. Based on our delivery in Bristol to young people being harmed in their communities through substance use, serious violence, and exploitation, we receive referrals showing a disproportionate percentage of racially minoritised young people. Following discussion with our referring partners in both LAs, we believe this pattern will be reflected in the MDFT pilot.

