Pre-test/ post-test	level 1 (participant)	0.40		
correlations	level 2 (cluster)	n/a		
Alpha ²		0.05		
Power		0.8		
One-sided or two-sided?		2-sided		
	Intervention	182		
Number of participants	Control	182		
	Total	364		

Outcome measures

To ensure outcomes are accessible to a wide range of potential participants we will make outcomes available in other languages, where validated and provide translators for other languages. As we anticipate a higher level of intellectual disability than the general population, we will seek the advice from the Tizard centre at the University of Kent who are specialists in the conduct of research with people with intellectual disabilities. We will seek advice on how outcomes can be presented to meet the needs of the target population; this will include using different fonts, colours, and the restriction on the amount of text presented on each page. The completion of outcomes will be supported with research staff available to address any questions. All outcome tools will be agreed with our youth advisory panel prior to use.

² Please adjust as necessary for trials with multiple primary outcomes, 3-arm trials, etc., when a Bonferroni correction is used to account for family-wise errors.

Baseline measures

Key demographic variables will be collected at baseline, these include DoB, sex, ethnicity, and index of material deprivation (IMD) derived from the participants postcode and converted to IMD using the IMD lookup tool:

https://geoconvert.ukdataservice.ac.uk/help/faq.html.

The severity of substance use, for stratification, will be determined by Global Assessment of Individual Need short screener for substance use (GAIN-SS; (Dennis et al., 2006)). This 5-item self-completed questionnaire has high sensitivity, 0.86, and specificity, 0.93, with an area under the curve of 0.97, in identifying adolescents who meet DSMIV criteria for low/moderate or severe substance use disorders. This outcome will be used as a stratification variable in the randomisation to ensure both groups have a similar distribution of low/moderate and severe cases.

Primary outcome

While the study will collect secondary outcomes on offending behaviour and delinquency, it is important to note the heterogeneity of the population is such that some participants will not be engaging in offending while all will have used substances. The proposed primary outcome for the study is frequency of substance use over a given period.

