Data from the internal pilot and efficacy study will be combined and analysed blind to group allocation. The efficacy analysis will follow CONSORT guidelines. The primary outcome is fractional, a proportion constrained by 0 or 1. The analysis will be conducted using an analysis by intention to treat and will include all available data to maintain participants as members of their allocated group, irrespective of what intervention was received, this provides an unbiased estimate of effect. To adjust for potential bias from recruiting participants to the pilot or efficacy stage, we will use an individual patient data meta-analysis, entering a dichotomous pilot/efficacy variable into the model as a fixed effect. Differences between the groups will be presented as marginal means and their associated 95% confidence intervals. If the missing primary outcome data exceeds 10% sensitivity analyses will be performed using a pattern mixture approach and multiple imputation to compare the sensitivity of conclusions to varying assumptions about the missing data, particularly whether data is missing at random (MAR) or missing not at random (MNAR) this allows for an assessment of both random and systemic bias.

Secondary outcomes will be assessed in a similar way by establishing diagnostic plots to identify the most appropriate regression approach, including stratification factors and baseline covariates within a multi-level model.

The primary end point is 6 months post-randomisation. This will allow an assessment of impact for short term outcomes. In order to explore whether effects are sustained over time and assess impact on longer term outcomes a secondary analysis will be conducted at 12-months post randomisation.

Exploratory analysis

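### The sample size and the stated primary model treat participants as independent although a planned seven therapists deliver MDFT, so the 80% power holds only if the therapist ICC is zero

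*Protocol*

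**What the plan says.** Delivery. The Participants section plans seven therapists: "This means that 4 therapists will be recruited in Bristol and 3 in Newport". The recruitment flow chart (Figure 3) shows each young person randomised to MDFT being allocated a therapist. The Business as usual section says that BAU comes from other services and that MDFT therapists take no part in it. Therapist is thus nested in one arm and not crossed with arm.

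Sample size. The text gives: "A clinically important effect size for substance use frequency in adolescents is estimated as 0.27", "with power at 80% and alpha of 0.05 and a two-tailed test". It then takes the pre-post-"test correlation of the frequency of substance use to be 0.4" and arrives at 364 followed up, 182 per group. Neither an ICC nor a number of therapists enters the calculation.

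Primary analysis. Under Efficacy study analysis: "The primary analysis will take the form of a fractional regression model, adjusted for baseline stratification variables and the baseline covariate". A fixed pilot/efficacy indicator is added in the next paragraph. Therapist is not among the listed terms, and no clustered variance is named.

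Elsewhere. The process evaluation plans a regression on the primary outcome that includes the influence of the interventionist. The pilot is to confirm or revise the sample size from the pre-post correlation (PRQ3) and an estimate of effect (PRQ4).

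**The concern.** Individual randomisation makes the arms comparable at baseline. It does not make outcomes independent after participants are assigned to a small number of therapists. If some therapists get better results than others, participants of the same therapist resemble each other, and the mean of the MDFT arm is less precise than 182 independent observations would make it. Adjusting for site removes differences between Bristol and Newport but not differences among therapists within a site.

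The protocol's own reasoning makes an ICC of exactly zero hard to assume. Appendix I describes MDFT as individualised psychotherapy and not a curriculum. The training section has therapists seeing young people from the start of their training. The process evaluation (Table 5) expects better alliance and communication with practitioners to go with better outcomes.

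Two things are at stake: a power statement that is too favourable and, if the analysis is run only as listed, a confidence interval that is too narrow and a false-positive rate above 5%.

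**Working it through.** **Inputs from the protocol.** Standardised effect d = 0.27; two-sided alpha 0.05; power 80%; pre-post correlation 0.4; 182 analysed per arm; k = 7 therapists.

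**Assumed, because the protocol does not give it.** Therapist ICC ρ = 0.01, 0.02 or 0.05, applied to the baseline-adjusted outcome, with equal caseloads. The calculation treats the outcome as a comparison of means on the standardised scale, as the protocol's own sample size does.

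**1. Reproduce the stated figure.** The residual variance after baseline adjustment is 1 − 0.4² = 0.84. Without adjustment, d = 0.27 needs 216 per arm, and 216 × 0.84 = 181.4, rounded up to 182 per arm or 364. (Direct calculation gives 181 per arm.) Power at 182 per arm is 80.2%. So 364 and 80% reproduce under independence. The intermediate statement, "requires a sample of 480 participants followed-up at the 6-month endpoint", does not reproduce, since 2 × 216 = 432. That is a separate matter and does not affect this point.

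**2. Clustering in the MDFT arm only.** Caseload m = 182/7 = 26. The MDFT design effect is DE = 1 + (26 − 1)ρ; the BAU design effect is 1.

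- Variance of the difference = (0.84/182) × (DE + 1).
- SE ratio, true to naive = √[(DE + 1)/2].
- The naive SE is too small by 1 − 1/ratio.
- Type I error of the naive test = 2 × [1 − Φ(1.96/ratio)].
- Power (normal) = Φ(0.27/SE − 1.96), where the naive SE is √(2 × 0.84/182) = 0.0961.
- Small-sample power uses a t reference with Satterthwaite df = (DE + 1)²/(DE²/6 + 1/181).

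| ρ | DE | SE ratio | Naive SE too small by | Naive type I error | Power, normal | df | Power, t |
|---|---|---|---|---|---|---|---|
| 0 | 1.00 | 1.000 | 0% | 5.0% | 80.2% | 23.2 | 76.8% |
| 0.01 | 1.25 | 1.061 | 6% | 6.5% | 75.5% | 19.0 | 71.0% |
| 0.02 | 1.50 | 1.118 | 11% | 8.0% | 71.0% | 16.4 | 65.7% |
| 0.05 | 2.25 | 1.275 | 22% | 12.4% | 59.7% | 12.4 | 52.9% |

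A simulation of 40,000 trials per setting, with normal data analysed without therapist, gave type I errors of 5.0%, 7.9% and 12.7% at ρ = 0, 0.02 and 0.05, in line with the table.

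**3. Sensitivity to the number of therapists.** Appendix I says a site team usually has six to eight therapists, which over two sites is 12 to 16. Power (normal) at ρ = 0.01 / 0.02 / 0.05 is 77.5% / 74.9% / 67.5% with 12 therapists and 78.2% / 76.3% / 70.7% with 16.

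**4. What 80% power would need with seven therapists.** The variance can be written 0.84(2 − ρ)/n + 0.84ρ/7. Setting it equal to (0.27/2.80)² and solving gives n = 207, 242 and 499 analysed per arm at ρ = 0.01, 0.02 and 0.05. The second term does not shrink as n grows, so extra participants become an inefficient remedy as ρ rises.

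**The case against.** **Table 3.** A reader might infer from the n/a at cluster level that the protocol ruled clustering out. It does not show that. The cell belongs to the row for pre-test/post-test correlations, is not a field for an ICC, and n/a is a proper entry there for an individually randomised trial.

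**The multi-level model.** A reader might also see an inconsistency in secondary outcomes being modelled "including stratification factors and baseline covariates within a multi-level model" while the primary is not. No levels are named; they could be time points, site or therapist. The same sentence says that secondary outcomes are handled in a similar way to the primary. It is not evidence about therapists either way.

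**The analysis plan may add it.** The protocol names a model family and covariates but no variance estimator, and a statistical analysis plan could add a therapist term. This stands in part: the type I figures describe the analysis as listed and are not a prediction for the trial. But an analysis plan cannot recover power that the sample size text has already claimed.

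**The pilot may revise the sample size.** It may, but the listed inputs are the correlation and the effect, not an ICC. With 30 MDFT pilot participants over seven therapists, about four each, an ICC would be poorly estimated anyway. The process-evaluation regression on interventionist influence does not change the primary interval.

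**The numbers are conditional.** This stands. The ICC is assumed, and seven is a plan: Appendix II allows therapists to be added, and turnover is foreseen. At ρ = 0.01 the effect is modest. The type I inflation also presumes that therapists represent a wider group; it would not arise for inference limited to these seven people. The sample size text, however, justifies the effect by commissioning in England and Wales, which reaches beyond them.

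**BAU may be clustered too.** Some BAU providers offer group or peer-group sessions. The figures here leave that out; any such correlation would add variance.

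**Conclusion.** The point holds. As written, the sample size and the primary model assume independence, and the stated 80% power is correct only at a therapist ICC of zero. With the planned seven therapists and equal caseloads, an ICC between 0.01 and 0.05 brings power down to between about 75% and 60%, or 71% and 53% with small-sample degrees of freedom. Part of that second range is the cost of the correction itself, which gives 76.8% even at a zero ICC. If therapist is left out of the analysis, the nominal 5% test runs at about 6.5% to 12%.

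The direction is firm for any positive ICC; the size is not, because it rests on an ICC the protocol does not give and on the number of therapists. More therapists soften the loss without removing it. The protocol does not support saying that clustering was explicitly dismissed, nor that the trial will certainly have an inflated error rate.

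**What to change.** 1. Make the primary analysis partially nested: a therapist random effect in the MDFT arm only, or variance clustered on therapist with each BAU participant as a singleton. Use a small-sample degrees-of-freedom correction in either case, since plain cluster-robust standard errors are unreliable with about seven clusters.
2. State the rule for MDFT participants who never start treatment. They stay in their arm under intention to treat, and the model needs to know how to code them, for example by the therapist allocated or as singletons.
3. In the sample size text, state the assumed ICC range, the number of therapists and the resulting power. This should not go in the correlation cell of Table 3.
4. Add the therapist ICC and the actual number of therapists to the inputs of the sample size review at the pilot transition, noting that the pilot alone will estimate the ICC poorly and that an assumed range will still be needed.

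The cost is wording, a wider confidence interval and a less favourable power statement. Therapist identity should be recoverable from the MDFT portal, where therapists record sessions, so little or no new data collection is expected. The analysis change needs no extra participants, but it does not bring power back to 80%. That would need more therapists, more participants or both, and should be weighed openly at the transition decision.
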